7.3 Endpoint Definitions

7.3.1 Primary Endpoint

- Establish MTD (Phase 1b)
- ORR (rate of CR and PR) by RECIST 1.1 in each cohort/group (Phase 2).

7.3.2 Secondary Endpoints

- Incidence and severity of AEs and specific laboratory abnormalities graded according to NCI-CTCAE, v4.03
- 6-month PFSR by cohort/group (Phase 2), defined as the proportion of subjects that did not have disease progression (by RECIST 1.1) or died due to any cause at 6 months from the first dose of investigational product
- DOR (by RECIST 1.1) by cohort/group, defined as the time from the first evidence of confirmed PR or better to disease progression or death due to any cause
- PFS (by RECIST 1.1) by cohort/group, defined as time from first dose of investigational product to the earlier of PD or death due to any cause.

7.3.3 Exploratory Endpoints

- PK parameters of APX005M, including C_{max} , time to maximum serum concentration (t_{max}), area under the curve at the last measurable time point (AUC_{0-t}), and $AUC_{0-\infty}$
- Presence and titer of anti-APX005M antibodies
- Association between potential PDn markers and PK of APX005M; association between potential predictive biomarkers and anti-tumor activity
- ORR by iRECIST in each cohort/group (Phase 2)
- DOR (by iRECIST) by cohort/group, defined as the time from the first evidence of confirmed PR or better to disease progression or death due to any cause
- PFS (by iRECIST) by cohort/group, defined as time from first dose of investigational product to the earlier of PD or death due to any cause

7.4 Analyses

7.4.1 Demographics and Baseline Characteristics

Demographics and baseline characteristics by cohort/group will be summarized using descriptive statistics.

7.4.2 Safety Analyses

Safety will be assessed through summaries of DLT, AEs, changes in laboratory test results, ECG, vital signs, and APX005M exposure. All AE data collected will be listed by study site, cohort, subject number, and cycle day.

The MTD is maximum dose for which <33% of DLT-evaluable subjects experience a DLT.

The RP2D will be taking into account the MTD of APX005M (if applicable), as well as the nature, severity and causal relationship for all AEs. Prior to establishing the RP2D all subjects enrolled in the phase 1 portion of the study must be followed until PD, study discontinuation due to toxicity or at least 2 cycles.

7.4.3 Efficacy Analyses

Tumor assessments by Investigator will follow RECIST 1.1 and iRECIST. ORR (and 90% confidence interval by exact distribution), DOR and PFS (Kaplan-Meier estimate) will be estimated for each cohort/group and for each tumor assessment method. Additional details will be provided in the Statistical Analysis Plan.

7.4.4 Pharmacokinetic Analyses

Blood samples will be collected from all subjects for determination of serum concentrations of APX005M at time points specified in [Section 5.6.1](#).

PK parameters of APX005M will be determined using model-independent methods. The following parameters will be calculated whenever practical:

Parameter	Description
t_{\max}	Time from the start of dosing at which the maximum concentration was observed.
C_{\max}	Maximum observed concentration.
C_{\max}/D	Dose-normalized C_{\max} .
AUC_{0-t}	Area under the concentration versus time curve from the start of dose administration to the last quantifiable point within the dosing interval.
$AUC_{0-\infty}$	Area under the concentration versus time curve for the dosing interval, using the trapezoidal rule.
$AUC_{0-\infty}/D$	Dose-normalized $AUC_{0-\infty}$.

When the concentration-time data permit, the slope of the terminal phase of each individual concentration versus time curve (λ_z) will be determined by log-linear regression for the first and third doses, and the following additional parameters will be estimated.

Parameter	Description
$t_{1/2}$	Terminal half-life.
$AUC_{0-\infty}$	Area under the concentration versus time curve from the start of dose administration to infinity, using the trapezoidal rule (first dose only).
CL	Total body clearance, calculated as $D/AUC_{0-\infty}$ (first dose only).
V_z	Terminal volume of distribution, calculated as CL/λ_z (first dose only).

Steady-state achievement will be assessed by comparing predose and end-of-infusion concentrations on Cycles 2, 3, and 4. Accumulation on Cycle 3 will be assessed by comparing $AUC_{0-\infty}$ and C_{\max} of the third and first doses and comparing predose concentrations of Cycles 3 to the predose sample of Cycle 2. Pharmacokinetic linearity will be examined by examining the

relationship between exposure (C_{max} , C_{max}/D , $AUC_{0-\infty}$, and $AUC_{0-\infty}/D$) with dose on the first and third doses.

Individual and mean serum concentration-time profiles will be tabulated separately for each dose by subject and nominal sampling time and summarized using descriptive statistics (mean and standard deviation). Pharmacokinetic parameters will also be summarized using descriptive statistics (mean and standard deviation) by dose and dosing day.

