5.1 Time and Events Schedule

Phase 1b Dose-escalation	Screening Phase (within 21 days prior to C1D1)	Treatment Phase									EOT (approx. 21 days after last treatment)	Follow- up
		Cycles 1 & 2					Cycles 3+					
Procedure	Day	1	2	3	8	15	1	8	2 nd Biopsy			
Written Informed Consent	X											
Inclusion/Exclusion Criteria	X	X										
Demographics	X											
Medical History	X											
Physical Examination	X	X					X				X	
Height	X											
Weight	X	X									X	
Vital Signs ^a	X	X	X	X	X	X	X	X			X	
12-lead ECG	X											
Urinalysis	X											
ECOG Performance Status	X	X					X				X	
Serum Chemistry ^b	X	X	X	X	X	X	X	X			X	
Thyroid Function Tests ^b	X						X					
Hematology Tests ^b	X	X	X	X	X	X	X	X			X	
Coagulation ^b	X	X			X	X	X	X			X	
PK Blood Tests ^c		X	X	X	X		X					
Immune PDn ^d		X	X	X	X		X	X	X		X	
Cytokines ^e		X	X	X	X		X	X	X		X	
AEs and ConMeds		X	X	X	X	X	X	X			X	X
Dosing Nivolumab		X					X					
Dosing APX005M		X					X					
Tumor Assessment ^f	X						X					X
Archived or Fresh Tumor Submission ^g	X											
Fresh Tumor Biopsy ^h	X								X			
ADA ⁱ		X					X				X	
Pregnancy Test (if applicable) ^j	X						X ^j					
Date of PD and Subsequent Therapy												X

Abbreviations: ADA = anti-drug antibodies; AE = adverse event; APTT = activated partial thromboplastin time; C1D1 = Cycle 1 Day 1; ConMeds = concomitant medications; ECG = electrocardiogram; ECOG = Eastern Cooperative Oncology Group; EOT = end of treatment; ICF = informed consent form; INR = international normalized ratio; PD = progressive disease/disease progression; PDn = pharmacodynamics; PK = pharmacokinetics; PT = prothrombin time; WOCBP = women of childbearing potential.

- ^a Vital signs: Vital signs measured within 30 min prior to nivolumab dose and at the end of the infusion, within 30 min prior to APX005M dose, end of the infusion, and 2 & 4 hours after infusion. All time points are \pm 30 min
- ^b Serum chemistry, hematology and coagulation tests performed at the local laboratory. Thyroid function tests performed every other cycle starting with Cycle 3
- ^c Blood samples for PK analyses collected in Cycles 1 and 2 before APX005M administration and at end of infusion, 4, 24 (Day 2), 48 (Day 3), and 168 hours (Day 8) from start of the infusion in that cycle. In addition, predose and end of infusion blood samples on Cycles 3 and 4 will be collected

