- f Optional fresh paired tumor core biopsies will be collected from consenting subjects prior to start of investigational products and prior to 1st scheduled tumor assessment. The biopsy should not interfere with the RECIST 1.1 tumor assessment. .
- g Blood samples for PK analyses collected every 3rd cycle (i.e., Cycles 1, 3, 6, 9, 12, etc) at predose and at end of infusion
- h Blood samples for anti-APX005M antibodies will be collected before dosing every 3rd cycle (i.e., Cycles 1, 3, 6, 9, 12, etc) and at the EOT visit
- i In WOCBP only, serum pregnancy test to be done within 7 days followed by a urine pregnancy test within 3 days of first dose of investigational product, or serum pregnancy test to be done within 3 days prior to first dose of investigational product. Pregnancy testing should be conducted every other cycle

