5.2.2 Treatment Phase

The following procedures and investigations should be performed during the Treatment Phase.

Day 1:

- Physical examination (including weight and vital signs)
- Determine ECOG performance status ([Appendix A](#))
- Record AEs and concomitant medication
- Laboratory evaluations (for Cycle 1, laboratory values from Screening Phase may be used if within 72 hours):
 - serum chemistry
 - thyroid function tests (every other cycle starting with cycle 3)
 - hematology
 - coagulation
- Collect blood samples for PK, ADA, cytokines and iPDn at designated timepoints ([Section 5.6](#))
- Administer premedication
- Administer nivolumab
- Administer additional premedication (if applicable)
- Administer APX005M
- Phase 1b dose-escalation collect blood samples for PK, PDn, and cytokines according to

schedule in [Section 5.6](#)

- Phase 2 dose-expansion collect blood samples for PDn, and cytokines according to schedule in [Section 5.6](#)
- Check criteria for discharge from clinic (see [Section 3.1](#))

Days 2 and 3 of Cycles 1 & 2 Phase 1b:

- Vital signs
- Record AEs and concomitant medication
- Laboratory evaluations:
 - serum chemistry
 - hematology
- In Phase 1b dose-escalation collect blood samples for PK, PDn, and cytokines according to schedule in [Section 5.6](#)

Day 8:

- Vital signs
- Record AEs and concomitant medication
- Laboratory evaluations (all test may be performed up to 24 hour in advance):
 - serum chemistry
 - hematology
 - coagulation
- Collect blood samples for PK, PDn, and cytokines according to schedule in [Section 5.6](#)

Day 15 of Cycles 1 and 2 Phase 1b:

- Vital signs
- Record AEs and concomitant medication
- Laboratory evaluations (all test might be performed up to 24 hour in advance):
 - serum chemistry
 - hematology
 - coagulation

Tumor assessments:

Tumor assessment will be performed within 21 days prior to start of investigational product and during Treatment Phase every 8 weeks \pm 1 week. Tumor response (CR or PR) or PD should be confirmed \geq 4 weeks later.

Optional Second tumor core biopsy:

From patients who have consented to the optional paired biopsy, fresh tumor core biopsies from the lesion selected at baseline will be collected prior to first scheduled tumor assessment (during Cycle 3, at approximately 7–8 weeks from first dose of investigational product).

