5.6.1 APX005M Pharmacokinetic Assessments

Phase 1b: Blood samples will be collected from all subjects at (relative to APX005M infusion):

- Cycles 1 & 2:
 - Day 1: predose, end of infusion and 4 hours after the start of the infusion
 - Day 2: 24 hours after the start of the infusion
 - Day 3: 48 hours after the start of the infusion
 - Day 8: 168 hours after the start of the infusion
- Cycles 3 & 4:
 - Day 1: predose and at end of infusion

Phase 2: Predose and at end of APX005M infusion blood samples will be collected every 3rd cycle (i.e., Cycles 1, 3, 6, 9, 12, etc.).

Details about collection procedure, volumes, and processing and shipping of PK samples are provided in the Laboratory Manual.

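### Protocol 7.4.4 plans a third-dose terminal slope, AUC accumulation and AUC linearity that the Cycle 3 PK samples cannot support: unobtainable in Phase 2, not interpretable in Phase 1b

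*Protocol*

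**What the plan says.** Protocol 7.4.4 takes its time points from Section 5.6.1 and asks for three things on the third dose:

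- **Terminal slope.** It "will be determined by log-linear regression for the first and third doses". This sentence is conditional on the data allowing it.
- **Accumulation.** AUC and Cmax are to be compared, in the words of the section, "of the third and first doses and comparing predose concentrations of Cycles 3 to the predose sample of Cycle 2".
- **Linearity.** Cmax, Cmax/D, AUC and AUC/D are to be related "with dose on the first and third doses".

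The parameter table in 7.4.4 is to be completed where practical. The accumulation and linearity sentences carry no such condition of their own.

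The sampling sections agree with one another:

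- Section 5.6.1, Phase 1b, Cycles 3 and 4: "Day 1: predose and at end of infusion".
- Section 5.1, Phase 1b schedule, footnote c: "predose and end of infusion blood samples on Cycles 3 and 4 will be collected".
- Section 5.1, Phase 2 schedule, footnote g: "Blood samples for PK analyses collected every 3rd cycle (i.e., Cycles 1, 3, 6, 9, 12, etc) at predose and at end of infusion".

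The visit text in Section 5.2.2, including Day 8, adds no sample. It says to "collect blood samples for PK, PDn, and cytokines according to schedule in" Section 5.6, which has no Cycle 3 Day 8 PK draw.

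SAP 2.2.3 and 5.4.4 leave PK to the sponsor or another provider. Section 7.4.4 is therefore the only PK specification in these documents.

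**The concern.** A log-linear slope needs several quantifiable concentrations after the peak, and a dosing-interval AUC needs samples across the interval. The full profile exists only in Phase 1b Cycles 1 and 2, yet the plan names the third dose. An analyst who follows 7.4.4 literally must either leave out named analyses without a stated replacement or compute a third-dose AUC from samples that do not describe the curve. In the second case the third/first ratio would be read as accumulation when it only reflects two different sampling grids. At stake are the repeat-dose half-life, AUC accumulation and AUC linearity that the protocol names for the combination.

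**Working it through.** **1. Scheduled PK samples (Protocol 5.1, 5.6.1).** Post-start means after the infusion begins. Residual df for a straight-line slope = post-start points − 2.

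| Phase, cycle | Samples | Post-start | Residual df |
|---|---|---|---|
| 1b, Cycles 1 and 2 | 6 each: predose, end of infusion, 4, 24, 48, 168 h | 5 | 5 − 2 = 3 |
| 1b, Cycles 3 and 4 | 2 each | 1 | 1 − 2 = −1 |
| 2, Cycles 1, 3, 6, 9, ... | 2 each | 1 | 1 − 2 = −1 |
| 2, Cycles 2 and 4 | 0 | 0 | none |

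**2. Part of the third-dose interval that is sampled.** The interval is 21 × 24 = 504 h. A nominal 60-minute infusion (3.3.2) gives 1/504 = 0.2%. It is longer if the infusion is interrupted or slowed (3.3.2). Table 4 of 3.7 includes a 90-minute infusion, for which 1.5/504 = 0.3%.

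**3. Borrowing the next predose sample.**

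- *Phase 1b:* the Cycle 4 predose sample closes the interval. It falls nominally at 504 h, or 504 − 72 = 432 h if drawn 72 h early (5.6). A single 3-day shift in dosing (3.3) widens this to 432 − 72 = 360 h and 504 + 72 = 576 h, and treatment delays extend it further. The slope then has 2 points and 0 residual df. Section 1.2.2 reports that levels at 0.1 to 1 mg/kg were mostly BLOQ between 24 and 168 h, so this sample would mostly be BLOQ.
- *Phase 2:* the next sample after Cycle 3 is the Cycle 6 predose, after further doses. Nothing can be borrowed.

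**4. What a borrowed AUC would show.** The documents give no human half-life, so I assumed a range of 6 to 72 h. The model is one-compartment with a 1 h infusion at unit rate and volume, and k = ln 2 / half-life:

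- C(t) = (1 − e^(−kt))/k for t ≤ 1, then C(1)·e^(−k(t−1))
- true AUC over 504 h = [1 − C(504)]/k
- sampled AUC = linear trapezoid on the stated grid

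Each AUC column gives the sampled AUC divided by the true AUC.

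| Half-life (h) | Third dose, 0 to 1 h only | Third dose, with Cycle 4 predose at 504 h | First dose, 6 samples | Apparent third/first ratio |
|---|---|---|---|---|
| 6 | 0.0546 | 27.49 | 1.308 | 27.49/1.308 = 21.0 |
| 12 | 0.0281 | 14.14 | 1.250 | 14.14/1.250 = 11.3 |
| 24 | 0.0142 | 7.17 | 1.221 | 7.17/1.221 = 5.9 |
| 48 | 0.0072 | 3.62 | 1.014 | 3.62/1.014 = 3.6 |
| 72 | 0.0048 | 2.45 | 0.856 | 2.45/0.856 = 2.9 |

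The model has no carry-over between doses, so a correct ratio would be 1. The departure from 1 comes entirely from the grid.

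**5. What the second dose offers.** Phase 1b Cycle 2 has 5 post-start samples. By Table 1 the contributors number at least 3 + 3 + 3 = 9 if all three escalation levels are completed without DL2a, or 12 with DL2a at its minimum. Approximately 18 are planned, and 3 to 6 at each of four levels would allow 24. Numbers fall if escalation stops early or subjects stop before Cycle 2. If the first BLOQ sample is at 24, 48 or 168 h, a subject has 2, 3 or 4 quantifiable post-start points, so only some will yield a slope.

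**6. Which AUC.** The same symbol is printed in 7.4.4 for two descriptions, which may be an artefact of the PDF. I read the accumulation and linearity sentences as meaning the one described as "Area under the concentration versus time curve for the dosing interval, using the trapezoidal rule", because the AUC to infinity is restricted to the first dose. The result is the same for either.

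**The case against.** The strongest reply is that the plan already protects itself. The slope is conditional on the data, and the AUC parameters are subject to practicality. A third-dose slope would simply not be produced, and the accumulation and linearity sentences would fall back on Cmax and predose values. Phase 1b Cycle 2 parameters would also be tabulated, because 7.4.4 summarises by dosing day. Further, PK is exploratory, Section 1.2.2 already reports no accumulation on a 21-day schedule, and the provider doing the PK work may have a specification that settles this.

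Much of this stands, and it limits the consequence. It does not remove the conflict. Those conditions suit subject-level gaps, whereas here the schedule rules out a usable result for everyone. Even if the practicality condition is carried over to the two unhedged sentences, the AUC part is dropped with no replacement named, and no Cycle 2 versus Cycle 1 comparison is planned. Section 1.2.2 itself calls the human PK data limited. The provider's specification is not in these documents.

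A reader might go further and infer that no subject in either phase could give these numbers. That holds for Phase 2 only. In Phase 1b the Cycle 4 predose sample makes a trapezoid arithmetically possible, and Section 1.2.2 says mostly BLOQ, not always. The right description there is not interpretable.

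**Conclusion.** The point holds as an internal contradiction between Protocol 7.4.4 and the sampling in 5.1 and 5.6.1. Third-dose slope, AUC accumulation and AUC linearity are unobtainable in Phase 2 and would be artefacts of the sampling grid in Phase 1b. The 2.5- to 27-fold figures rest on the assumed half-lives and model. The sample counts do not.

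The consequence is confined to exploratory PK. Two wider inferences are not supported:

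- *That repeat-dose PK as a whole is lost.* Third-dose Cmax and Cmax/D remain feasible in both phases, as do the Phase 1b predose and end-of-infusion comparisons across Cycles 2, 3 and 4.
- *That the sampling schedule, or the dose label, is shown to be the mistake.* The documents do not say which. They show only that the two must be reconciled.

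**What to change.** Reconcile 7.4.4 with 5.6.1:

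1. Remove the third-dose slope and third-dose AUC analyses. Limit Cycles 3 and 4 to end-of-infusion and predose concentrations.
2. Assess AUC accumulation from Phase 1b Cycle 2 versus Cycle 1, within subject, over a common quantifiable window reported by dose level. Dose-normalise the ratio, because Section 3.7 allows the APX005M dose to be reduced between cycles.
3. Assess repeat-dose AUC linearity on the Phase 1b second dose, by dose actually given.
4. Fit the second-dose terminal slope only where a minimum number of quantifiable points, stated in advance, is met.
5. State which AUC each sentence means.

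Step 1 alone would remove the contradiction, but it would leave no planned repeat-dose AUC comparison.

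The change is to text and adds no blood draws. An amendment needs IRB/IEC approval (8.1.2), whereas for an administrative letter the IRB/IEC is informed (8.1.1). The sponsor must judge which applies. If amending is no longer practical, put the change in the PK provider's specification and record the departure from 7.4.4.

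The price is that AUC accumulation is judged after two doses rather than three, and in few subjects. SAP Section 7 notes that the final Phase 1b report has been done, without showing whether it covered PK. If it did, the second-dose analysis should be labelled post hoc.

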7.4.5 Exploratory Analyses

Potential tumor and blood biomarkers identified in the exploratory biomarker research may be correlated with PK, safety, and efficacy outcomes.

8. Administrative Section

8.1 Ethics

8.1.1 Compliance with the Protocol and Protocol Revisions

This study will be conducted in accordance with this study protocol and with ICH GCP guidelines, the United States Code of Federal Regulations, Title 21, Part 50 (21CFR50), as well as all other applicable country and regional legal and regulatory requirements. The Investigator is responsible for ensuring that this protocol, the site's ICF, and any other information that will be presented to potential subjects are reviewed and approved by the appropriate IRB/IEC prior to the enrollment of any study subjects.

If an amendment substantially alters the study design or increases the potential risk to the subject:

1. The consent form must be revised and submitted to the IRB/IEC for review and approval/favorable opinion
2. The revised consent form must be used to obtain consent from subjects currently enrolled in the study if they are affected by the amendment
3. The new consent form must be used to obtain consent from new subjects prior to enrollment

If the revision is an administrative letter, Investigators must inform their IRB/IEC.

8.1.2 Institutional Review Board/Independent Ethics Committee

The Investigator must obtain written and dated approval/favorable opinion from the IRB/IEC for the protocol, consent form, subject recruitment materials/process (e.g., subject leaflets), and any other written information to be provided to subjects. The Investigator or sponsor should also provide the IRB/IEC with a copy of the Investigator Brochure or product labeling, information to be provided to subjects and any updates. Amendments to the protocol must also be approved by the IRB/IEC prior to the implementation of changes in this study.

The Investigator or sponsor should provide the IRB/IEC with reports, updates, and other information (e.g., expedited safety reports, amendments, and administrative letters) according to regulatory requirements or institution procedures.

8.1.3 Informed Consent

Written informed consent is required from each subject prior to any testing under this protocol, including screening tests and evaluations. The ICF, as specified by the clinical site's IRB/IEC, must follow the Protection of Human Subjects regulations listed in the CFR, Title 21, Part 50.

Investigators must ensure that subjects or, in those situations where consent cannot be given by subjects, their legally acceptable representative, are clearly and fully informed about the purpose, potential risks, and other critical issues regarding this clinical study in which they volunteer to participate. The information that is given to the subject or the representative shall be in a language understandable to the subject or representative. Freely given written informed consent prior to clinical study participation must be obtained from every subject or, in those situations where consent cannot be given by subjects, their legally acceptable representative, including informed consent for any screening procedures conducted to establish subject eligibility for the study.

If a subject is unable to read or if a legally acceptable representative is unable to read, an impartial witness should be present during the entire informed consent discussion. After the written ICF and any other written information to be provided to subjects, is read and explained to the subject or the subject's legally acceptable representative, and after the subject or the subject's legally acceptable representative has orally consented to the subject's participation in the trial and, if capable of doing so, has signed and personally dated the ICF, the witness should sign and personally date the consent form. By signing the consent form, the witness attests that the information in the consent form, and any other written information, was accurately explained to, and apparently understood by, the subject or the subject's legally acceptable representative, and that informed consent was freely given by the subject or the subject's legally acceptable representative.

Preparation of the consent form is the responsibility of the Investigator and must include all elements required by ICH, GCP and applicable regulatory requirements as well as adhere to GCP and ethical principles that have their origin in the Declaration of Helsinki. The consent form must also include a statement that sponsor and Regulatory Authorities have direct access to subject records. Apexigen (or designee) will provide the Investigator with a sample consent form.

Prior to the beginning of the study, the Investigator must have the IRB/IEC's written approval/favorable opinion of the written ICF and any other information to be provided to the subjects. The Investigator must provide the subject or legally acceptable representative with a copy of the consent form and allow time necessary for subject or subject's legally acceptable representative to inquire about the details of the study, then informed consent must be signed and personally dated by the subject or the subject's legally acceptable representative and by the person who conducted the informed consent discussion.

The subject or legally acceptable representative should receive a copy of the signed informed consent and any other written information provided to study subjects prior to subject's participation in the trial.

